Urine collection for pharmacokinetics			X	X	X		Participants with normal hepatic function and participants with hepatic impairment will have different collection intervals See Table 2 for time points
Saliva collection for pharmacokinetics			X	X	X		See Table 2 for time points
AE/SAE review	X	X	←=====→			X	
Concomitant medication review		X	←=====→			X	

AE = adverse event, Clcr = estimated creatinine clearance; ECG = electrocardiogram, FDA = Food and Drug Administration; FSH = follicle-stimulating hormone; HIV = human immunodeficiency virus; PGx = pharmacogenetic, SAE = serious AE; WOCBP = women of childbearing potential.

¹ When coinciding with safety and/or pharmacokinetic assessments, electrocardiograms, vital signs, and pharmacokinetic blood collections should be performed in said order.

Table 2 Safety and PK Assessments

Procedure ¹	Predose	Treatment Period Time point (hours)													
		0	0.5	1	1.5	2	2.5	3	4	6	8	12	24 ²	36 ²	48 ²
12-lead electrocardiogram	X				X	X			X		X	X	X	X	X
Vital signs	X				X	X			X		X	X	X	X	X
Study drug administration		X													
Blood collection for pharmacokinetics	X		X	X	X	X	X	X	X	X	X	X	X	X	X
Urine collection for pharmacokinetics (participants with normal hepatic function) ³	X	X			X			X	X	X	X	X	X	X	X
Urine collection for pharmacokinetics (participants with hepatic impairment) ⁴	X	X						X		X	X	X	X	X	X
Saliva collection	X		X	X	X	X	X	X	X	X	X	X	X	X	X

¹ When coinciding with safety and/or pharmacokinetic assessments, electrocardiograms, vital signs, and pharmacokinetic blood collections should be performed in said order.

² The 24-, 36-, and 48-hour postdose time points correspond to time points on Day 2 and 3, respectively.

³ Urine collection intervals for participants with normal hepatic function (Group D and Group E, if applicable) include 0 (pre-dose), 0 to 2 hours, 2 to 4 hours, 4 to 6 hours, 6 to 8 hours, 8 to 12 hours, 12 to 24 hours, 24 to 36 hours, and 36 to 48 hours.

⁴ Urine collection intervals for participants with hepatic impairment (Group A, Group B, and Group C) include 0 hour (pre-dose), 0 to 6 hours, 6 to 12 hours, 12 to 24 hours, 24 to 36, and 36 to 48 hours.

- The timing and number of planned study assessments, including: safety and pharmacokinetic assessments may be altered during the course of the study based on newly available data (e.g., to obtain data closer to the time of peak plasma concentrations) to ensure appropriate monitoring.

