10. Participants must abstain from taking prescription or nonprescription drugs (including vitamins and dietary or herbal supplements), unless specified in Section 7.7.1, within 7 days (or 14 days if the drug is a potential strong enzyme inducer) or 5 half-lives (whichever is longer) prior to study drug administration until completion of the Follow-Up Visit, unless, in the opinion of the investigator and Sponsor, the medication will not interfere with the study. Any exceptions (including participants with hepatic impairment that will be on medications during the study) will be discussed with the sponsor or medical monitor on a case-by-case basis and the reasons will be documented.

Prior/Concurrent Clinical Study Experience

11. Previous exposure to gepotidacin within 12 months prior to study drug administration.
12. The participant has participated in a clinical trial and has received an investigational product within the following time period prior to study drug administration in the current study: 30 days, 5 half-lives, or twice the duration of the biological effect of the investigational product (whichever is longer).

Diagnostic Assessments

13. Participant with normal hepatic function has presence of hepatitis B surface antigen or positive hepatitis C antibody test result at Screening or within 3 months prior to study drug administration. Participant with hepatic impairment has evidence of recent, acute infection with hepatitis B and/or hepatitis C within preceding 6 months. Hepatically impaired participants with chronic hepatitis B or C (duration >6 months) are eligible for enrolment.
14. A positive test for human immunodeficiency virus antibody.
15. Participant must be able to abstain from alcohol and limit use of nicotine and/or nicotine-containing products (up to 5 cigarettes/day is acceptable for participants with hepatic impairment) for 24 hours before the start of dosing until after collection of the final PK sample. A positive alcohol or cotinine test is not exclusionary for participants with hepatic impairment.
16. Participant has clinically significant abnormal findings in serum chemistry, hematology, or urinalysis results obtained at Screening or Day -1, other than those associated with underlying hepatic conditions or other stable medical conditions consistent with the disease process in participants with hepatic impairment.

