7.2. Secondary Pharmacokinetic Analyses

7.2.1. Endpoint / Variables

7.2.1.1. Drug Concentration Measures

Refer to [Appendix 3: Data Display Standards & Handling Conventions \(Section 10.3.3 Reporting Standards for Pharmacokinetic\)](#)

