7.2.1.2. Derived Pharmacokinetic Parameters

Pharmacokinetic parameters will be calculated by standard non-compartmental analysis according to current working practices and using the currently supported version of WinNonlin. All calculations of non-compartmental parameters will be based on actual sampling times.

Plasma pharmacokinetic parameters listed below will be determined from the total plasma concentration-time data, as data permits.

Parameter	Parameter Description
AUC(0-t)	Area under the concentration-time curve from time 0 (predose) to time of last quantifiable concentration, to be calculated using the linear trapezoidal rule for each incremental trapezoid and the log trapezoidal rule for each decremental trapezoid
Tmax	Time to first occurrence of Cmax
tlag	Lag time before observation of drug concentrations in sampled matrix
t _{1/2}	Terminal half-life will be calculated as: $t_{1/2} = \ln 2 / \lambda_z$
λ_z	Terminal-phase rate constant
CL/F	The apparent oral clearance, calculated as: $CL/F = \text{Dose} / AUC(0-\infty)$
Vz/F	The apparent volume of distribution during the terminal phase, calculated as: $V_z/F = CL / \lambda_z$

NOTES:

- Additional parameters may be included as required.
- For the derivation of unbound plasma PK parameters; the total plasma PK parameters AUC(0-t) will be multiplied by 0.67, and the total plasma PK parameter CL/F will be divided by 0.67, to correct for the low plasma protein binding of gepotidacin (33%) observed in previous studies.

Pharmacokinetic parameters listed will be determined from the urine concentration-time data, as data permits.

Parameter	Parameter Description
Ae total	Total unchanged drug (total amount of drug excreted in urine), calculated by adding all the fractions of drug collected over all the allotted time intervals
Ae(t1-t2)	Amount of drug excreted in urine in time intervals for predose, 0 to 6, 6 to 12, 12 to 24, 24 to 36, and 36 to 48 hours after dosing for subjects with hepatic impairment; and predose, 0 to 2 hours, 2 to 4 hours, 4 to 6 hours, 6 to 8 hours, 8 to 12 hours, 12 to 24 hours, 24 to 36 hours, and 36 to 48 hours for subjects with normal hepatic function; calculated by multiplication of the urine concentration for a time interval and the length of this time interval.

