AUC(0-t)	Area under the urine concentration-time curve over t hours where t = 12, 24, and 48 hours. The AUC(0-t) will be calculated by the linear trapezoidal rule based on the urine concentration data from each collection interval versus the corresponding urine collection interval.
Fe%	Percentage of the given dose of drug excreted in urine, calculated as: $fe\% = (Ae \text{ total}/\text{Dose}) \times 100$
CLr	Renal clearance of drug, calculated as: $CLr = Ae \text{ total}/AUC(0-t)$ where AUC(0-t) is the area under the plasma concentration-time curve over all the allotted time intervals of urine collections.

NOTES:

- Additional parameters may be included as required.

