7.2.4.1. Statistical Methodology Specification

Endpoint / Variables

 Plasma secondary PK endpoints include AUC(0-t), T_{max}, t_{lag}, CL/F, λ_z, and t_{1/2}, as data permit. Urine primary PK endpoints include AUC(0-48) and CL_r of gepotidacin, as data permit. Urine secondary PK endpoints include Ae(t₁-t₂), AUC(0-12), AUC(0-24), and AUC(0-48) of gepotidacin, as data permit
Model Specification

 The plasma T_{max} will be analyzed non-parametrically using the Mann Whitney U test (Wilcoxon rank sum test). The point estimates and 90% CI for the median differences will be derived for hepatic impairment and healthy participants based on Hodges-Lehmann estimation. The urine ln-transformed AUC(0-48) and non-transformed CL_r values for gepotidacin in the hepatic impairment groups and the normal hepatic function group will be compared using an analysis of variance (ANOVA).
Model Checking & Diagnostics

 Model assumptions will be applied, but appropriate adjustments may be made based on the data.
Model Results Presentation

 The point estimates and 90% confidence intervals for the median differences in plasma T_{max} will be calculated for the cohort difference (hepatically impaired – healthy participants). Statistical analysis by ANOVA will be presented in tabular format with geometric mean ratios between hepatic impairment groups and normal hepatic function group, and 90% CIs for the ratios of AUC(0-48) for gepotidacin. For non-transformed CL_r for gepotidacin, least squares mean difference between hepatic impairment groups and normal hepatic function group, and 90% CIs for the difference will be presented.

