10.1.2. Protocol Defined Safety and PK Assessments

Procedure ¹	Predose	Treatment Period Time point (hours)													
		0	0.5	1	1.5	2	2.5	3	4	6	8	12	24 ²	36 ²	48 ²
12-lead electrocardiogram	X				X	X			X		X	X	X	X	X
Vital signs	X				X	X			X		X	X	X	X	X
Study drug administration		X													
Blood collection for pharmacokinetics	X		X	X	X	X	X	X	X	X	X	X	X	X	X
Urine collection for pharmacokinetics (participants with normal hepatic function) ³	X		X	X	X	X	X	X	X	X	X	X	X	X	X
Urine collection for pharmacokinetics (participants with hepatic impairment) ⁴	X				X					X	X	X	X	X	X
Saliva collection	X		X	X	X	X	X	X	X	X	X	X	X	X	X

¹ When coinciding with safety and/or pharmacokinetic assessments, electrocardiograms, vital signs, and pharmacokinetic blood collections should be performed in said order.

² The 24-, 36-, and 48-hour postdose time points correspond to time points on Day 2 and 3, respectively.

³ Urine collection intervals for participants with normal hepatic function (Group D and Group E, if applicable) include 0 (pre-dose), 0 to 2 hours, 2 to 4 hours, 4 to 6 hours, 6 to 8 hours, 8 to 12 hours, 12 to 24 hours, 24 to 36 hours, and 36 to 48 hours.

⁴ Urine collection intervals for participants with hepatic impairment (Group A, Group B, and Group C) include 0 hour (pre-dose), 0 to 6 hours, 6 to 12 hours, 12 to 24 hours, 24 to 36, and 36 to 48 hours.

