10.3.3. Reporting Standards for Pharmacokinetic

Pharmacokinetic Concentration Data	
Descriptive Summary Statistics, Graphical Displays and Listings	
Refer to IDSL PK Display Standards. Refer to IDSL Statistical Principle 6.06.1.
 
For continuous data:
 
 NQs at the beginning of a participant profile (i.e. before the first incidence of a measurable concentration) are deemed to be zero as it is assumed that in this circumstance no drug is yet measurable in the blood. For NQs at the end of the participant profile (i.e. after the last incidence of a measurable concentration); 
 for individual plots and pharmacokinetic analyses these are dropped (set to missing) as they do not provide any useful information (and can erroneously indicate that absolutely no drug is present) for summary statistics, these are set to 0 (to avoid skewing of the summary statistics) Individual NQs which fall between two measurable concentrations are set to missing (individual values of this nature are assumed to be an anomaly) 
If two or more NQ values occur in succession between measurable concentrations, the profile will be deemed to have terminated at the last measurable concentration prior to these NQs. For the purpose of individual participant plots, these NQs will be set to 0, and the subsequent measurable concentrations will be retained. For the derivation of pharmacokinetic parameters, these NQs and any subsequent measurable concentrations will be omitted (set to missing).
 
Note: Concentration values will be imputed as per GUI_51487 for descriptive summary statistics/analysis and summarized graphical displays only.

Pharmacokinetic Parameter Data	
Descriptive Summary Statistics, Graphical Displays and Listings	
N, n, geometric mean, 95% CI of geometric mean, standard deviation (SD) of logged data and between geometric coefficient of variation (CV_b (%)) will be reported.
 $CV_b (\%) = \sqrt{(\exp(SD^2) - 1) * 100}$ 
(SD = SD of Ln-Transformed data)

Parameters Not Being Ln-Transformed	T _{max} , t _{lag} , CL _r , lambda _{z_lower} , lambda _{z_upper} , and lambda _{z_no.} of points.
Parameters Not Being Summarized	lambda _{z_lower} , lambda _{z_upper} , and lambda _{z_no.} of points.
Listings	Include the first point, last point and number of points used in the determination of λ _z and R _{sq_adjusted} for listings.

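### Urine AUC(0-48) is compared between groups whose urine is collected on different early intervals, so the trapezoidal ratio mixes the collection scheme with hepatic function

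*SAP*

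**What the plan says.** **Collection schedules.** The SoA (Protocol section 2, Table 2 footnotes) and SAP 10.1.2 agree. For controls the intervals are "Group D and Group E, if applicable) include 0 (pre-dose), 0 to 2 hours, 2 to 4 hours, 4 to 6 hours", then 6-8 and 8-12 h. For impaired participants SAP 10.1.2 has "Urine collection intervals for participants with hepatic impairment (Group A, Group B, and Group C) include 0 hour (pre-dose), 0 to 6 hours", then 6-12 h. SAP 7.2.1.2 repeats the impaired list as "predose, 0 to 6, 6 to 12, 12 to 24, 24 to 36, and 36 to 48 hours after dosing". From 12 h on, both groups share 12-24, 24-36 and 36-48 h.

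**Derivation.** SAP 7.2.1.2 says the urine AUC "will be calculated by the linear trapezoidal rule based on the urine concentration data from each collection interval versus the corresponding urine collection interval". It does not say whether an interval's concentration is placed at the start, midpoint or end. SAP 10.8.7 specifies the midpoint, but only for plots.

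**Predose value.** SAP 7.2.1.1 refers to "Section 10.3.3 Reporting Standards for Pharmacokinetic", which states that "NQs at the beginning of a participant profile (i.e. before the first incidence of a measurable concentration) are deemed to be zero". A predose urine collection is scheduled, and Protocol 6.2 excludes "Previous exposure to gepotidacin within 12 months prior to study drug administration", so predose urine should be non-quantifiable.

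**Comparison.** SAP 7.2.4.1 takes "The urine ln-transformed AUC(0-48) and non-transformed" renal clearance into an ANOVA and reports a geometric mean ratio with 90% CI for AUC(0-48); Protocol 10.3.1 says the same. The objectives tables list AUC(0-48) as a secondary urine endpoint, although SAP 7.2.4.1 also lists it with the urine primary ones. Neither document harmonises the intervals before the comparison.

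**The concern.** A trapezoid through interval-averaged concentrations depends on where the intervals lie. If two groups have the same urine concentration curve but it is averaged over different intervals, the rule returns two different areas. The schedule is tied completely to hepatic status, so the ANOVA cannot separate the two effects, and more participants would not help.

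If the artefact pushes the ratio down, no difference would look like a reduction and a true rise in impaired participants would be understated. The shift is systematic, so the reported 90% CI does not reflect it.

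**Working it through.** **1. The plan's own figure.** No urine ratio or urine variability is stated. The only precision figure is for plasma (Protocol 10.1), with 8 per group. The CI upper limit lies exp(t(0.95, 14 df) x sqrt(ln(1 + CV²)) x sqrt(2/8)) - 1 above the estimate. CVs of 23.4%, 22.9% and 43.6% give 22.55%, 22.03% and 44.40%, against 22.5%, 22.0% and 44.4% stated. This reproduces.

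**2. Node weights, identical kinetics, constant flow, zero at time 0.** At constant flow C(0-6) = [C(0-2) + C(2-4) + C(4-6)]/3 and C(6-12) = [C(6-8) + 2 x C(8-12)]/3.

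Weight in hours given to each fine-interval concentration:

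| | 0-2 | 2-4 | 4-6 | 6-8 | 8-12 | 12-24 |
|---|---|---|---|---|---|---|
| Midpoint, control | 1.5 | 2 | 2 | 2.5 | 5.5 | 10 |
| Midpoint, impaired | 1.5 | 1.5 | 1.5 | 2.5 | 5 | 10.5 |
| End, control | 2 | 2 | 2 | 3 | 8 | 12 |
| End, impaired | 2 | 2 | 2 | 3 | 6 | 12 |

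Later weights are equal. Control area minus impaired area is therefore:
- midpoints: 0.5 x [C(2-4) + C(4-6) + C(8-12) - C(12-24)], positive for any profile that has declined by 12-24 h;
- interval ends: 2 x C(8-12), positive whenever drug is present.

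**3. Worked case** (assumed: absorption rate 1/h, half-life 6 h, no lag; highest control value = 100). Controls: 70.8, 100, 85.3, 68.5, 48.9, 20.8, 5.2, 1.3. Impaired: 85.4, 55.4, 20.8, 5.2, 1.3.
- Midpoints with zero: 1088.4/1195.1 = 0.911. The gap is 106.7 = 0.5 x (100 + 85.3 + 48.9 - 20.8).
- Share from the first trapezoid at midpoints: rising from zero removes 1.5 h x 85.4 = 128.1 from the impaired area but 0.5 h x 70.8 = 35.4 from the control area. The difference, 92.7, is 87% of the gap (84% to 95% over all parameter sets).
- Ends with zero: impaired 256.2 + 422.4 + 457.2 + 156 + 39 = 1330.8; control 70.8 + 170.8 + 185.3 + 153.8 + 234.8 + 418.2 + 156 + 39 = 1428.7; ratio 0.931. The gap, 97.9, is 2 x 48.9 within rounding.

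**4. Range over assumed kinetics, constant flow.** The 69 parameter sets are 60 monoexponential (absorption 0.5-2.5/h, half-life 2-10 h, lag 0 or 0.5 h) and 9 biexponential. The true ratio is 1.

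| Placement and handling before the first node | Impaired/normal |
|---|---|
| Midpoint, predose zero | 0.849-0.942 |
| End, predose zero | 0.921-0.975 |
| Midpoint, first value carried back | 0.984-0.995 |
| End, first value carried back | 1.010-1.193 |
| Interval start | 0.699-0.966 |
| Concentration x interval length | 1.000 |

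A separate grid with half-lives up to 20 h gave 0.855-0.966 (midpoint, zero) and 0.920-0.974 (end, zero). Leaving out the time before the first node altogether gave about 0.69-0.94. The worked case at midpoints becomes (1088.4 - 128.1)/(1195.1 - 35.4) = 0.828.

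**5. Varying flow, predose zero.** Nine patterns of early flow gave 0.689-0.969 (midpoints) and 0.782-0.999 (ends). Other patterns pass 1 at interval ends. With absorption 2.5/h and half-life 2 h, flow x0.67 in 4-6 h gives 1.006, and x0.5 in 4-6 h with x2 after 6 h gives 1.011.

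**6. A real difference** (impaired half-life 1.25 to 2.0 times control; true ratio 1.22-1.97). Estimated/true ratio:

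| | Own grids, constant flow | Pooled, constant flow | Pooled, nine flow patterns |
|---|---|---|---|
| Midpoint | 0.896-0.924 | 0.965-1.034 | 0.959-1.092 |
| End | 0.864-0.948 | 0.934-1.005 | 0.929-1.047 |

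Further runs with varying flow reached about +11% at midpoints after pooling.

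**7. Against precision.** If urine AUC had the plasma CV of 22.9% (an assumption), the log half-width of the 90% CI would be 0.199. The step 4 shifts are -ln(0.942) = 0.060 to -ln(0.849) = 0.164 at midpoints and -ln(0.975) = 0.025 to -ln(0.921) = 0.082 at ends, that is 30%-82% and 13%-41% of that half-width.

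**The case against.** **The predose zero is a reading of the SAP.** The rule in SAP 10.3.3 sits under a label for summaries, graphs and listings, is justified by drug in blood, and is followed by a note limiting one imputation guideline to summaries. Against that, the section also covers PK analyses and parameter derivation, and SAP 7.2.1.1 sends urine data there. The reading is plausible but not explicit, and stands here as an assumption.

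**Time placement may be settled elsewhere.** SAP 7.2.1.2 defers to current working practices, WinNonlin and actual sampling times. One can say only that neither document states it.

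**The wording is loose enough to mean concentration times interval length,** which SAP 7.2.1.2 uses for amount excreted and which gives 1.000 at constant flow. But the SAP names the trapezoidal rule for AUC, and the rectangle version ranges over 0.797-1.023 across the nine flow patterns.

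**The consequence is limited.** This stands. Ae total, fe% and renal clearance do not use the urine trapezoid. Neither Part 2 entry criterion names urine AUC, and Protocol 10.3.4 frames the review on plasma PK. Under the CV assumption the shift is smaller than the CI half-width.

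**Two stronger readings are tempting and fail.** A reader might infer that the ratio is always below 1; step 5 shows small excesses at interval ends, and step 4 larger ones without the predose zero. A reader might also infer that the first trapezoid explains the bias generally. That holds at midpoints; at interval ends the first 6 h carry equal weight in both groups and the whole gap is 2 x C(8-12).

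**Conclusion.** The concern holds for the between-group comparison of urine AUC(0-48). As written, the rule gives a ratio other than 1 for identical kinetics. With constant flow and the predose zero the ratio is too low by about 6% to 15% at midpoints and 2.5% to 8% at interval ends. The direction in that setting follows from the trapezoid weights for any profile that has declined by 12-24 h; the sizes rest on assumed kinetics and are ranges, not estimates. Varying flow usually lowers the ratio further, with exceptions of about 1% above 1 at interval ends. Without the predose zero, direction depends on the time placement and on how the area before the first node is treated.

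The summarised but untested AUC(0-12) and AUC(0-24) share the artefact (0.783-0.927 and 0.902-0.975 at ends, zero, constant flow). The documents do not support extending it to plasma AUC(0-∞) or Cmax, which use one schedule, or to the Part 2 entry criteria. Nor need it exclude 1 from the CI by itself. It should be corrected before any urine comparison is reported.

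**What to change.** Before any between-group urine AUC comparison, including the Part 1 interim output (SAP 10.8.6, Table 3.8), amend SAP 7.2.1.2 to:
- pool each control's collections onto 0-6, 6-12, 12-24, 24-36 and 36-48 h, with pooled concentration = sum of (concentration x urine volume) / sum of volumes;
- apply the same linear trapezoid in all groups, state that the predose zero applies to urine, and state one time placement (for example the midpoint already used in the plots) with a rule for closing the area to 48 h;
- keep the fine-grid control data for description.

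With identical kinetics and flow, both groups then have the same nodes and weights, and the ratio is exactly 1.000.

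**Cost.** SAP wording and one derivation step; collection does not change, because the impaired boundaries are already among the control boundaries. Confirm in the SRM that interval volumes are recorded: Protocol 9.5.2 mentions only date and time and leaves details to the SRM. If they are not, time-weighted pooling is possible but exact only at constant flow.

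**Downside.** The controls' early detail drops out of the comparison. Pooling removes the grid effect only. When profiles differ in shape and flow varies, an error of several percent, up to roughly 10% at midpoints, can remain. Differences in urine flow between groups still act on a urine-concentration AUC: with identical kinetics, impaired flow at 0.8 times control gives 1/0.8 = 1.25 after pooling.

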10.3. Statistical Analyses

10.3.1. Pharmacokinetic Analyses

Plasma and urine concentrations of gepotidacin will be subjected to PK analyses using noncompartmental methods. Based on the individual concentration time data the following parameters will be estimated:

Plasma:

AUC(0-∞)	Area under the concentration-time curve from time 0 (predose) extrapolated to infinite time
AUC(0-t)	Area under the concentration-time curve from time 0 (predose) to time of last quantifiable concentration
Cmax	Maximum observed concentration
λ_z	Terminal-phase rate constant
t _{1/2}	Terminal phase half life
Tmax	Time to first occurrence of Cmax
t _{lag}	Lag time
CL/F	Apparent oral clearance

V_z/F Apparent volume of distribution

Urine:

Ae total Total unchanged drug (total amount of drug excreted in urine), calculated by adding all the fractions of drug collected over all the allotted time intervals

Ae(t1-t2) Amount of drug excreted in urine in a time intervals for predose, 0 to 6, 6 to 12, 12 to 24, or 24 to 36, and 36 to 48 hours after dosing for participants with hepatic impairment; and predose, 0 to 2 hours, 2 to 4 hours, 4 to 6 hours, 6 to 8 hours, 8 to 12 hours, 12 to 24 hours, 24 to 36 hours, and 36 to 48 hours for participants with normal hepatic function

fe% Percentage of the given dose of drug excreted in urine, calculated as:

$$fe\% = (Ae \text{ total}/Dose) \times 100$$

CL_r Renal clearance of drug, calculated as: $Ae \text{ total}/AUC(0-t)$

AUC(0-12) Area under the concentration-time curve from time 0 (predose) to 12 hours

AUC(0-24) Area under the concentration-time curve from time 0 (predose) to 24 hours

AUC(0-48) Area under the concentration-time curve from time 0 (predose) to 48 hours

Plasma concentrations and urine concentrations of gepotidacin and the associated PK parameters will be listed, and summary statistics (n, mean, median, standard deviation [SD], minimum, maximum, and coefficient of variation [CV]) will be presented by day and treatment. Mean and individual plasma concentration versus time profiles will be presented graphically on linear and semilogarithmic scales.

The natural log-transformed plasma AUC(0-∞) and C_{max} values for gepotidacin in the hepatic impairment groups and normal hepatic function groups will be compared using an analysis of variance. Geometric mean ratios between hepatic impairment groups and normal hepatic function groups, and 90% CIs for the ratios of AUC(0-∞) and C_{max} for gepotidacin will be presented.

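### CLr divides the drug collected by plasma AUC over all scheduled urine intervals, so a wholly missed interval, if left out of the sum, lowers CLr, Ae total and fe%

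*SAP*

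**What the plan says.** - **Numerator.** SAP 7.2.1.2 defines Ae total as the total drug excreted in urine, "calculated by adding all the fractions of drug collected over all the allotted time intervals". fe% is this quantity divided by dose.
- **Denominator, SAP.** CLr is Ae total divided by the "area under the plasma concentration-time curve over all the allotted time intervals of urine collections". On the schedule this is 0 to 48 h.
- **Denominator, protocol.** Protocol 10.3.1 divides Ae total by AUC(0-t), defined for plasma as "Area under the concentration-time curve from time 0 (predose) to time of last quantifiable concentration". SAP Table 1, which lists changes from the protocol, does not mention the difference.
- **Ae per interval.** The SAP says it is "calculated by multiplication of the urine concentration for a time interval and the length of this time interval". Urine volume does not appear.
- **Schedules** (SAP 10.1.2, footnotes 3 and 4). Impaired participants have five post-dose collections: "0 to 6 hours, 6 to 12 hours, 12 to 24 hours, 24 to 36, and 36 to 48 hours". Controls have eight: "0 to 2 hours, 2 to 4 hours, 4 to 6 hours, 6 to 8 hours, 8 to 12 hours", then the same three 12-hour intervals from 12 to 48 h.
- **Missing data.** SAP 10.5.2 says how blanks are displayed and how partial dates are treated. SAP 10.3.3 deals with non-quantifiable concentrations. Neither mentions a missed or incomplete urine collection. The PK Parameter population (SAP 4) requires usable parameters but does not say what makes a urine parameter usable.

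**The concern.** Renal clearance is drug excreted over a period divided by plasma exposure over the same period. Here the numerator depends on what was collected, while the denominator is fixed by the schedule or by the plasma assay. A missed interval takes drug out of the first and nothing out of the second, and the result reads as lower renal clearance.

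CLr is listed among the primary urine endpoints in both documents. It is compared between groups by ANOVA on the untransformed scale, with a least squares mean difference and 90% CI (protocol 10.3.1, SAP 7.2.4.1), so one participant's error passes straight into a group mean of about eight. The severe group may close with six. The CLr ANOVA (SAP Table 3.8) is also an interim deliverable. Protocol 3.1 describes elimination as mainly parent drug in urine, so an artefactual fall in CLr could be taken for a real renal effect.

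**Working it through.** The plan states no precision or completeness figure for CLr, Ae total or fe%, so there is nothing of its own to reproduce.

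**Step 1. Formula.** With constant true CLr, Ae in an interval equals CLr times plasma AUC in that interval. If one interval is missed and left out of the sum:

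reported CLr / true CLr = 1 − AUC(missed interval) / AUC(0-48)

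Ae total and fe% fall by the same proportion relative to complete 0-48 h recovery. This takes Ae as a true amount. Under the SAP's concentration-times-length formula the same shares apply only if urine flow is constant.

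**Step 2. Inputs.** The intervals are from SAP 10.1.2 and the group size of 8 is from protocol 10.1. Half-life and absorption rate are *assumptions*, because the documents give neither: half-life 4, 8 or 12 h and ka 0.7 or 1.5 per hour, in a one-compartment oral curve proportional to exp(−kt) − exp(−ka·t), with k = ln 2 / half-life.

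**Step 3. Share of AUC(0-48) in each impaired-schedule interval (%).** This is the fall in CLr if that interval is missed.

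| Half-life, ka | 0-6 h | 6-12 h | 12-24 h | 24-36 h | 36-48 h |
|---|---|---|---|---|---|
| 4 h, 0.7 | 53.5 | 29.9 | 14.5 | 1.8 | 0.2 |
| 4 h, 1.5 | 60.0 | 25.8 | 12.4 | 1.5 | 0.2 |
| 8 h, 0.7 | 32.9 | 27.8 | 26.6 | 9.4 | 3.3 |
| 8 h, 1.5 | 37.5 | 26.0 | 24.7 | 8.7 | 3.1 |
| 12 h, 0.7 | 24.8 | 24.1 | 29.2 | 14.6 | 7.3 |
| 12 h, 1.5 | 28.3 | 23.0 | 27.8 | 13.9 | 7.0 |

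**Step 4. Effect on a group mean.** With equal CLr, one miss among 8 shifts the mean by one eighth of the share. For 0-6 h this is 24.8/8 = 3.1% to 60.0/8 = 7.5%; for 36-48 h it is 0.2/8 = 0.03% to 7.3/8 = 0.9%. In a group of 6, one 0-6 h miss shifts the mean by 24.8/6 = 4.1% to 60.0/6 = 10%.

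**Step 5. Controls.** Their early intervals are shorter, so one miss costs less: 5.5-21% (0-2 h), 10-23% (2-4 h) and 10-18% (4-6 h).

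**Step 6. Expected loss over the whole schedule.** Suppose each collection is missed with the same probability p. The expected proportional loss is p times the sum of the interval shares, and the shares sum to 1 on either schedule. For 8 h and ka 1.5, the impaired shares are 37.5 + 26.0 + 24.7 + 8.7 + 3.1 = 100, and the control shares are 11.2 + 14.1 + 12.1 + 10.2 + 15.8 + 24.7 + 8.7 + 3.1 = 99.9, which is 100 up to rounding. The expected loss is therefore p in both groups. No difference is created where none exists; a true difference is shrunk by the factor 1 − p.

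**Step 7. Incomplete collection.** Suppose 30% of the 0-6 h volume is lost. With Ae as concentration times volume, CLr falls by 0.3 times the 0-6 h share: 0.3 × 24.8% = 7% to 0.3 × 60.0% = 18%. With the SAP formula as written, volume is not used and nothing changes.

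**Step 8. Matched denominator.** Dividing Ae over the collected intervals by plasma AUC over those same intervals returns 1.000 of true CLr in every scenario where a missed interval was run (0-6, 6-12 and 36-48 h). With the SAP denominator the ratio is 0.40-0.75, 0.70-0.77 and 0.93-0.998 respectively.

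**The case against.** Numerator and denominator are both described over the scheduled intervals, so by design they match, and Ae total can be read as requiring every interval. Parameters are derived only where the data allow, and the analysis population asks for usable ones. A pharmacokineticist could properly set CLr to missing. **This stands in part:** the plan does not say that a missed interval counts as zero, so the bias is a risk from an unstated rule. But the proviso is not defined for urine, and the decision would be taken with the data in view in an open-label study.

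A reader might infer two stronger claims, which the documents do not support.

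- **Any incomplete collection lowers CLr.** Under the SAP's written formula, volume lost within a sampled interval has no effect (Step 7). That formula does not yield an amount and needs correcting, but until it is corrected only wholly missed intervals matter.
- **The longer impaired-schedule intervals bias the comparison toward lower CLr in impairment.** This looks at the cost of one miss and forgets that controls have eight chances to miss against five. Step 6 shows equal expected loss at equal miss rates. Grade 1 or 2 encephalopathy is compatible with entry, so a higher miss rate in impaired participants is plausible, but no rate is given.

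Two further points limit the importance. Participants are confined from Day -1 to Day 3, so the whole 48 h collection takes place in the clinic, and handling details sit in a reference manual outside these documents. CLr also serves a secondary objective; the primary endpoints are plasma AUC(0-∞) and Cmax.

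**Conclusion.** The point holds in limited form. The CLr definition does not tie its numerator and denominator to the same completed intervals, the protocol and SAP use different denominators, and no rule covers a missed urine interval. If a missed interval is left out of the sum, that participant's values fall by about 25-60% (0-6 h), 23-30% (6-12 h), 12-29% (12-24 h), 1.5-15% (24-36 h) or 0.2-7% (36-48 h) on the impaired schedule.

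These ranges rest on the assumed half-life and absorption rate, a one-compartment curve and constant true CLr. How often collections will be missed is unknown. Longer intervals raise the cost and the variability of each miss; a spurious group difference needs the groups to miss collections at different rates.

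The change is worth making before the Part 1 interim. It removes the bias if missed intervals would be omitted, and it keeps a participant in a group of six to eight if CLr would otherwise be dropped.

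**What to change.** 1. In SAP 7.2.1.2 and protocol 10.3.1, define CLr as the sum of Ae over completely collected intervals divided by the sum of plasma AUC over those same intervals. State how the partial AUC is taken when plasma is no longer quantifiable before an interval ends.
2. Correct Ae per interval to urine concentration times urine volume in the same revision.
3. Do not present Ae total and fe% to 48 h as complete when an interval is missing. Either set them to missing, or report them to the last complete interval and label them so. Choose one rule now.
4. List missed and incomplete collections by group, with a count alongside SAP Table 3.5.

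**Cost:** wording changes and partial AUCs in the planned noncompartmental run. Plasma is already sampled at 2, 4, 6, 8, 12, 24, 36 and 48 h, the end of every urine interval on both schedules, so no new samples are needed. The downside is that some Ae total and fe% values will be missing or truncated.
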